2.1 Study Rationale

Peanut allergy (PA) is a common and potentially life threatening condition for which the only current approved management involves strict dietary avoidance. Oral immunotherapy (OIT) is a promising investigational treatment option for this condition, and multiple published studies have demonstrated efficacy in achieving successful desensitization to peanut in children with peanut allergy.⁸⁻¹⁶ However, the widespread clinical use of OIT has been limited by numerous factors. These include the high rate of adverse events (AEs), including anaphylaxis, which often leads to high subject drop-out rates in published studies (Table 1). These studies all used peanut products produced by roasting methods, including flour, peanut powder, or peanut butter. Published data have demonstrated that boiling peanut results in reduced allergenicity while preserving the immunogenicity necessary to produce tolerance.¹⁹ In this pilot study, we plan to compare the use of boiled peanut OIT to published data on roasted peanut OIT in children with peanut allergy. Based on currently available data, we hypothesize that the subjects treated with this novel regimen of boiled peanut will demonstrate lower rates of adverse events while demonstrating similar immunologic markers of peanut desensitization and possible tolerance compared to published data on subjects treated with OIT utilizing a traditional roasted peanut product.

2.2 Background and Significance

Peanut allergy (PA) has a reported prevalence of 2% in children and 0.7% in adults.¹ The prevalence of PA also appears to be increasing, and in a registry of fatal food induced anaphylaxis, 63% of the 32 fatalities were caused by peanut.² The implications of PA extend beyond the patient and their family. This food allergy in particular has impacted the educational system as well as the food industry.³ The effect on quality of life can be significant,^{4,5} often leading to social isolation and even fear of death. Currently standard of care for PA consists of allergen avoidance, which is often ineffective, and administration of emergency medications on accidental exposure.⁶ Given the prevalence of PA and its associated morbidities, safe and effective therapies are desperately needed.

Immunotherapy relies on the delivery of increasing doses of specific allergens over time with the goal of developing desensitization, which increases the dose of protein needed to elicit an allergic response.

Over the past century, immunotherapy has been successfully used to treat asthma, allergic rhinitis, and insect venom anaphylaxis through subcutaneous or sublingual administration. Although the exact mechanisms underlying allergen immunotherapy are still not fully understood, it is known to induce allergen-specific regulatory T cells, which suppress TH2 responses that promote IgE production. This response is coupled with increases in serum concentrations of allergen-specific IgG4 antibodies which compete with IgE on cell surfaces and result in reductions in mast cell and basophil activation and mediator release.⁷ An increased IgG4 to IgE ratio is associated with clinical tolerance to a given food.

Though immunotherapy can be administered in a variety of methods, oral immunotherapy (OIT) has shown the most promise in the treatment of food allergy. Several recent trials have utilized the technique of oral immunotherapy for treatment of peanut and other food allergies. This therapy involves mixing the food allergen into a vehicle of choice and having the subject begin daily consumption while gradually increasing the dose. Several endpoints have been defined when evaluating the response to immunotherapy. Desensitization results in a higher threshold for an allergic reaction, typically above the amount that will be encountered in an accidental exposure. However, this does require ongoing dosing. The most desirable outcome of OIT is sustained unresponsiveness, or continued long term tolerance of the food without the need for daily maintenance therapy.

Although individual responses vary considerably, OIT will induce significant desensitization in most subjects who are able to tolerate the therapy. However, these studies are limited by frequent treatment related AEs and high rates of withdrawal due to these AEs. The reported AEs and dropout rates from representative studies are outlined in Table 1.⁸⁻¹⁶

There is a large amount of heterogeneity in the reporting of AEs. More specifically, AEs are at times reported in terms of the percent of subjects experiencing an adverse reaction. At other times, adverse reactions are reported in terms of the percent of doses that cause an AE. This method is often utilized to report AEs during maintenance dosing. This is in part due to the fact that over the course of all phases of an individual study and when including mild AEs in addition to more significant reactions, nearly 100% of patients have some form of AE during treatment. Thus it may be more meaningful to report the percent of doses causing symptoms at times.

Table 1: Prior OIT Trials

Author	N	Age	Design	Adverse Events	Drop outs	Additional Detail on Drop Outs
Jones et al 2009 [8]	39	1-16	Open label	92% of subjects on initial escalation day, 46% doses during build up, 3.7% doses during maintenance	10 (25%)	4 withdrew for allergic effects and 6 for personal reasons
Hofmann et al 2009 [10]	28	1-16	Open label	93% of subjects on initial escalation day, 46% doses during build up, 3.5% of doses during maintenance	5 (18%)	3 withdrew following initial escalation, 1 during build up, 1 during maintenance
Blumchen et al 2010 [9]	23	3-14	Randomized, open label	7.8% of doses during rush protocol, 2.9% of doses during maintenance	8 (35%)	1 during rush protocol, 7 during long term buildup of which 4 for allergic side effects
Varshney et al 2011 [11]	19	1-16	Double blind, placebo controlled	47% subjects with "clinically relevant" AEs during initial escalation day, 1.2% doses during build up	3 (16%)	2 withdrew during initial escalation day and 1 after first build up dose
Anagnostou et al	22	4-18	Open label	86% subjects during build up and maintenance	1 (5%)	Withdrew after the first up dose at home

2011 [12]						
Anagnostou et al 2014 [13]	99	7-16	Randomized, placebo controlled cross over	6.3 % of all doses	7 (7%)	5 withdrew for allergic reactions or persistent symptoms, 1 disliked taste, and 1 no specific reason
Vickery et al 2014 [14]	39	1-16	Open label	Previously reported in pilot study (Jones et al 2009)	15 (38%)	6 withdrew due to allergic side effect and 9 for personal reasons
Narisety et al 2014 [15]	21	7-13	Randomized, double blind, placebo controlled	43% doses during blinded phase (escalation and maintenance), 36.7% doses in OIT group during unblended phase	7 (33%)	1 withdrew after initial escalation, 1 during build up and 3 during maintenance. 1 drop out on SLIT with placebo OIT
Vickery et al 2016 [16]	37	9-36 months	Randomized, double blind, low and high dose	95% patients during entire study, 0.8% doses during study	5 (14%)	2 withdrew for nonadherence, 1 for recurrent emesis and 1 for EoE

Abbreviations: N, number of subjects, AEs, adverse events, SLIT, sublingual immunotherapy, OIT, oral immunotherapy, EoE, eosinophilic esophagitis

Given the high rate of these treatment related AEs such as oral itching, stomach upset and other GI complaints, and occasional serious systemic allergic reactions requiring the use of injectable epinephrine, OIT is still considered an experimental treatment. While some major medical centers and a number of private practice allergists offer peanut OIT to their patients, it is not yet FDA approved.

A commercially developed product, AR101 (Aimmune Therapeutics), an investigational oral biologic drug, was recently trialed in a phase 3 study evaluating efficacy. In the intervention group, 67.2% of patients ages 4–17 tolerated at least a 600-mg dose of peanut protein in the exit food challenge, compared to 4.0% of placebo patients ($p < 0.00001$). In the trial's primary analysis group of ages 4–17, 496 patients from both arms (372 AR101 and 124 placebo) were evaluable for safety. In both arms, the incidence of serious adverse events (SAEs) was low. A total of 10 patients experienced SAEs, none of which were considered life-threatening: nine of these patients were in the AR101 arm (2.4%) and one was in the placebo arm (0.8%). Of the nine AR101 patients who experienced a SAE, five patients experienced mild or moderate SAEs. The other four AR101 patients experienced severe SAEs, which, for two of these patients, were not related to treatment (a concussion and a viral asthmatic exacerbation). Of the two patients who experienced severe SAEs related to treatment, both of whom had elevated baseline peanut-specific IgE levels greater than 100 kU/L, one experienced anaphylaxis, and the other experienced wheezing on the first day of treatment. Both of these patients discontinued from the study. In ages 4–17, 20.4% of AR101 patients and 6.5% of placebo patients discontinued the trial. In the AR101 arm, 12.4% of patients discontinued due to investigator-reported adverse events, including 6.7% due to gastrointestinal adverse events and 2.7% due to systemic allergic hypersensitivity reactions. In the placebo arm, 2.4% of patients discontinued due to investigator-reported adverse events (Table 2).²⁸

Table 2: Discontinuations in the AR101 Group²⁸

	AR101 (n= 372)	
	%	n
Total discontinuations regardless of causality	20.4%	76
Discontinuations not related to adverse events	8.0%	30
Discontinuations related to adverse events	12.4%	46
• Gastrointestinal ²	6.7%	25
• Systemic hypersensitivity reactions ³	2.7%	10
• Respiratory system	1.1%	4
• Cutaneous	0.8%	3
• Other	1.1%	4

We seek to identify a means of accomplishing peanut desensitization while decreasing the rate of treatment related AEs. It has been shown that standard roasting methods of peanut preparation can play a significant role in increasing the undesirable allergenic properties of peanuts.¹⁷ It has also been demonstrated that peanut antigen stimulation of peripheral blood T lymphocytes is unaffected by various heating methods, which is necessary for induction of tolerance.¹⁸ An additional study confirms the findings of extended boiling resulting in reduction of peanut allergenicity while preserving the effect on T cell reactivity.¹⁹ A group recently reported a series of 4 subjects with peanut allergy who were treated with daily doses of boiled peanut, one of which subsequently transitioned to raw peanut. All subjects demonstrated lower IgE reactivity to boiled peanut compared to control suggesting that in vivo findings correlate with the prior in vitro data.²⁰

While OIT is a promising therapy, we hypothesize that by treating peanut allergic subjects with a peanut product of reduced allergenicity but preserved T cell reactivity, we will be able to desensitize these subjects to a target maintenance dose of peanut protein with reduced rates of allergen associated AEs, while preserving immunologic effects that will promote tolerance. This will confirm that the immunologic changes produced by roasted peanut OIT can be replicated more safely using boiled peanut. If successful, such a therapy will decrease the number of subjects that must discontinue this treatment due to related AEs, and offer a potentially important therapy for this life threatening condition. Improved safety of this intervention may also allow for higher treatment doses to be used, may allow inclusion of more severely allergic subjects excluded from previous trials, and possibly increase the likelihood for attainment of permanent tolerance with sustained unresponsiveness, rather than perpetuating the need for continual daily dosing. This will likely result in the eventual inclusion of BPOIT in general Allergy/Immunology practice as a treatment for peanut allergy. We suspect this therapy will improve quality of life as measured by validated questionnaires as well as, or better than, roasted peanut oral immunotherapy.²⁸

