1.1 Study Synopsis

Title: Boiled Peanut Oral Immunotherapy

Study Description: Prospective Phase 1 clinical trial providing proof of concept data on boiled peanut oral immunotherapy (OIT) for the treatment of peanut allergy in children. We hypothesize that the proportion of subjects successfully desensitized with boiled peanut OIT is greater than the theoretical placebo rate of 20%.

Objectives:

- Determine the effect of boiled peanut immunotherapy on the immune response to peanut.
- Compare the safety and tolerability of boiled peanut oral immunotherapy to published data on roasted peanut oral immunotherapy in pediatric subjects with confirmed IgE mediated peanut allergy.
- Primary endpoint: Response to treatment defined as ability to successfully consume a single dose of 300 mg or greater of peanut protein with no dose limiting symptoms at exit double blind placebo controlled food challenge (DBPCFC).
- Secondary endpoints:
- Maximum dose achieved with no or minimal symptoms at exit DBPCFC.
- Change in the maximum tolerated dose from screening to exit DBPCFC.
- The rate of side effects of treatment defined as oral itching, rhinorrhea, conjunctivitis, urticaria, angioedema, abdominal upset, vomiting, diarrhea, cough, wheeze, or anaphylaxis.
- Change in quality of life scores before and after treatment utilizing validated, age specific, food-related quality-of-life surveys before and after peanut oral immunotherapy (Supplement 1)
- Peanut protein component panel, to determine the presence of high levels of sensitivity to peanut proteins known to be associated with severe systemic reactions (Arah 1,2,3) versus mild reactions (Arah8).

Endpoints:

- Levels of peanut specific serum IgG4, with higher levels associated with increased tolerance to peanut protein.

Study Population:

Children ages 1-16 with peanut allergy suggested via history of reaction and objective evidence of IgE mediated hypersensitivity either via skin testing or in vitro testing (peanut specific IgE concentration) within the last 12 months.

Inclusion criteria:

[figure not shown]
- Age 1-16 years
- History of immediate hypersensitivity reaction to peanut or a high level of suspicion based on testing at the discretion of the investigator
- Evidence of IgE mediated peanut hypersensitivity within a 12 month period of study enrollment including:
 - Skin prick test with wheal diameter of at least 3mm and/or
 - Peanut specific IgE >0.35 ku/L

Exclusion criteria:

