2.3 Risk/Benefit Assessment

2.3.1 Known potential risks

There is a significant rate of adverse reactions with peanut oral immunotherapy in clinical trials to date. Mild adverse reactions such as oral itching or nausea are reported in up to 10-15% of all doses. Over the course of an individual study, this reaches nearly 100% of all subjects. The rate of these adverse events are outlined in representative studies in Table 1.

More severe reactions requiring treatment with epinephrine or inhaled beta-agonists are less frequent but can occur. In a large review of multiple centers performing peanut OIT, Wasserman et al noted a total of 95 adverse reactions requiring epinephrine in 352 patients that collectively received more than 240,000 doses of peanut.²⁵ The results of the largest peanut OIT trial to date, a phase 2 clinical trial utilizing product AR101 were published in March of 2018.²¹ In this study, 9 (14%) of 63 subjects received a single injection of epinephrine during initial double blind placebo controlled food challenge (DBPCFC) at screening: 4 were randomized to AR101, 4 to placebo, and 1 was not enrolled. For the duration of maintenance therapy, one treatment subject received a single epinephrine injection for moderate anaphylaxis at home. Finally, during the exit DBPCFC, 11 of 26 placebo subjects (42%) were administered epinephrine and 2 of 23 AR101 subjects (9%) received a single injection of epinephrine.

Across the various peanut OIT trials, there has been no specific statistical analysis examining adverse reaction rate or withdrawal rate at various ages. Presumably this is due to the fact that no specific age related pattern has emerged and that anaphylaxis and subject withdrawal has occurred in subjects of all ages.

There is also a risk for development of Eosinophilic Esophagitis (EoE). A recent review estimated the prevalence across the OIT clinical trials as 3-4% and in the study conducted by Bird et al, EoE occurred in only 1 subject (<5%) from the treatment group.²¹ Once OIT is discontinued in these patients, the EoE typically resolves.

There is also a risk of causing anxiety or stress in the subject or the family. The impact of oral immunotherapy on quality of life has been examined with a variety of foods. Quality of life in patients with food allergy improves in some but declines in others while undergoing OIT, and in particular tends to decline in those rating a higher quality of life prior to initiation of the treatment.²⁶

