8.3 Covariates and Subgroups

No subgroup analyses are planned.

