11.1.2 Comparative AE table

AE data from this study will be compared descriptively to the AE data from three published studies: the study medication arms of the Phase 2 and Phase 3 trials of AR101 OIT for peanut allergy (Bird et al., 2018; Vickery et al. for PALISADE, 2018), and OIT data from the PACE meta-analysis study of OIT for peanut allergy (Chu et al., 2019). No hypothesis testing will be performed.

For this table, study AEs will be categorized into two study phases as best corresponds to the comparative data: 1) initial dose escalation study visit, and 2) an increasing dose phase which includes all other dose escalation study visits and home doses, but excludes the exit DBPCFC. AEs will be grouped into severity grades, treatments, and preferred terms, where the preferred term list will include the specific AEs of interest only (see sections 5.2 and 9.2.3). (Refer to mock Table 3.3 for comparative data and source information.)

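### The comparative AE table sets boiled-peanut children aged 1-16 beside a Phase 3 AR101 group aged 4-17, so age mix cannot be separated from an effect of boiling; a column for ages 4 and over would help

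*Protocol*

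**What the plan says.** **Population.** Protocol 1.1 describes the study population as "Children ages 1-16 with peanut allergy suggested via history of reaction". Protocol 5.1 and SAP 6.2 give the same age range.

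**Comparators.** SAP 11.1.2 states: "AE data from this study will be compared descriptively to the AE data from three published studies". Two of these are "the study medication arms of the Phase 2 and Phase 3 trials of AR101 OIT for peanut allergy"; the third is "OIT data from the PACE meta-analysis study of OIT for peanut allergy". The boiled-peanut side is the whole Safety Population (SAP 14, Table 3.3). The table is descriptive, with no hypothesis test.

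**Comparator ages.** For Phase 3, Protocol 2.2 writes: "In the trial's primary analysis group of ages 4–17, 496 patients from both arms (372 AR101 and 124 placebo) were evaluable for safety". The ages in the Phase 2 trial and in the meta-analysis appear in neither document.

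**Handling of age.** SAP 8.3 reads: "No subgroup analyses are planned". Age at the initial oral food challenge (OFC) is derived in SAP 9.2.4 and summarised for the Safety population in SAP 9.3, but AEs are not to be shown by age.

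**Position on age and AEs.** Protocol 2.3.1 says of earlier peanut OIT trials that "there has been no specific statistical analysis examining adverse reaction rate or withdrawal rate at various ages". It then presumes that this is because no age pattern has been seen.

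**The concern.** The secondary objective is to compare AE rates with published roasted-peanut data, and SAP 11.1.2 is where that is done. The trial has a single arm, so a reader has only the likeness of the columns to go on. Children aged 1-3 can enter the boiled-peanut column but not the Phase 3 one. If AE rates differ by age, part of any difference between those columns may come from who was enrolled and not from how the peanut was prepared. The protocol's reassurance that age does not matter rests on the absence of an analysis, not on a result. What is at stake is how a descriptive table is read; no test, error rate or power figure is affected.

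**Working it through.** **1. Overlap of ages.** Boiled peanut: 1-16 years (Protocol 1.1, 5.1). Phase 3 AR101: 4-17 years, with a safety count that adds up (372 + 124 = 496). Ages 1, 2 and 3 are open to enrolment here and absent there. The documents give no expected age mix. If ages were spread evenly over the 16 single years, 3/16 × 10 = 1.9, or about 2 of the 10 children, would be under 4. That spread is an assumption; the number could be 0.

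**2. Does the protocol's own evidence give a direction?** The inputs are from Protocol Table 1. The row for ages 9-36 months reads "95% patients during entire study, 0.8% doses during study". For older children the table gives 6.3% of all doses in the study in ages 7-16, and 86% of subjects in the study in ages 4-18.

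Suppose k of 10 children take the rate of the youngest study and the rest take the older rate, with equal doses per child and no effect of boiling:

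- Per dose: (k × 0.8 + (10 − k) × 6.3) / 10
- Per patient: (k × 95 + (10 − k) × 86) / 10

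| k | Per dose | Per patient |
|---|---|---|
| 0 | 6.3% | 86.0% |
| 2 | 5.2% | 87.8% |
| 4 | 4.1% | 89.6% |
| 5 | 3.55% | 90.5% |

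The per-dose rate falls as k rises and the per-patient rate goes up, so the same table points both ways. The per-patient contrast is itself weak. The nearest whole counts are 35/37 and 19/22, and Fisher's exact test on them gives a two-sided p of 0.35. It does not establish a reverse pattern, but it does prevent a claim that the bias must be downward.

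**3. Can the gap between those studies be put down to age?** Table 1 has three studies in ages 1-16 that report build-up rates: 46%, 46% and 1.2% of doses. The ratio is 46 / 1.2 = 38 with the age range held fixed. Differences in product, design and AE definition can therefore be far larger than the 0.8% versus 6.3% contrast, and that contrast cannot be assigned to age.

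**4. Do the step 2 figures describe the planned table?** No. None of the studies in step 2 is named as a comparator in SAP 11.1.2. The figures show direction only and are not an estimate of bias in Table 3.3.

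**5. Precision of a restricted column.** With 9 of 10 children having an AE, the Clopper-Pearson 95% interval is 55.5% to 99.7%. With about 8 children left, 7 of 8 gives 47.3% to 99.7%. The restricted column improves comparability but will not show whether age matters.

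**The case against.** The strongest reply is that this is a descriptive table in a 10-patient proof-of-concept study. Phase 3 is only one of three comparators, age is tabulated for the Safety population so readers will see the mix, and dropping about two children leaves too few to learn from. Most of that stands, and it is why the point is minor. It does not remove the mismatch: an age summary elsewhere in the report does not let a reader take the youngest children out of the AE rates.

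Three stronger readings are tempting, and the documents support none of them.

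- *The youngest children will lower the boiled-peanut rate.* A reader might infer this from the 0.8% figure. The same row gives 95% of patients, and step 2 shows the direction reversing.
- *The bias is 17% to 44%.* These are the per-dose falls from 6.3% at k = 2 and k = 5: 1 − 5.2/6.3 = 17% and 1 − 3.55/6.3 = 44%. They contrast two studies outside SAP 11.1.2 and assume the whole gap is due to age. The larger figure also needs half the sample to be under 4.
- *Age-matched evidence has been left out, so the Table 1 studies in ages 1-16 should be added.* They are not named comparators, but the meta-analysis may include some of them; the documents do not list its component studies. Adding them is also a doubtful gain. Two have 46% build-up rates, which could flatter boiled peanut. A third counts only clinically relevant events on the escalation day, and the fourth refers back to the first for its AEs.

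**Conclusion.** The concern holds in a limited form. Boiled-peanut children aged 1-3 have no counterpart in the Phase 3 AR101 column, and the plan offers no way to separate age mix from an effect of boiling there. Neither the direction nor the size of any bias can be stated from the documents.

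This rests on two conditions: that some children under 4 are in fact enrolled, and that mock Table 3.3, which was not available for this review, does not already split by age. Nothing is shown about the Phase 2 or meta-analysis columns, whose ages are not given. Severity: minor, a cheap improvement to how the table can be read.

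**What to change.** In SAP 11.1.2 and mock Table 3.3:

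- Keep the all-ages boiled-peanut column.
- Add a descriptive column for children aged 4 or older at the initial OFC, using the age derived in SAP 9.2.4, and state that it is the one to read against the Phase 3 AR101 column. Give its number of children.
- Read it against the Phase 2 column as well only if that trial's published age range also starts at 4; check this before the table is fixed.
- In SAP 8.3, exempt this one column from the statement that no subgroups are planned. Add no test.
- The Table 1 studies need not become columns.

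The cost is one column and two or three sentences in the SAP, with no new data. The downside is that the column has fewer than 10 children whenever any aged 1-3 enrol, so its rates will be imprecise. If none enrol, the two columns coincide and can be merged.
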